7.2.5 Immunology Peripheral Blood Processing

7.2.5.1 Peripheral blood Analysis of Changes in Immune Cell Subsets, T-Cell Repertoire, and Cytokines

Flow cytometry for immune cell subsets. (primarily T-cell subsets) will be performed in the Human Immune Monitoring Core (HIMC) at UC Davis. Expression levels determined by MFIs for markers will be compared at baseline and on treatment.

These: subsets will include:

- T cell subset panel: CD4, CD8, CD3, CD25, CD127, Foxp3 (ICS)
- T cell differentiation panel: CD4, CD8, CD3, CD45RA, CCR7 (extras: CD45RO, CD44)
- T cell exhaustion panel: CD4, CD8, CD3, PD-L1, PD-1, TIM3, (extras: LAG3, 2B4, CD160)
- T cell activation panel: CD4, CD8, CD3, HLA-DR, Fas, GranzB (ICS), CD28 (extras: ICOS, CD40L, FasL)

Luminex Assay for measurement of cytokines (25 plea) in plasma and supernatant after activation with CD3+ CD28 or PMA+Ionomycine will also be performed in the HIMC at UC Davis. (http://tools.lifetechnologies.com/content/sfs/manuals/LHC0009_Protocol.pdf).

7.2.5.2 Peripheral Blood Collection for Changes in Immune Subsets

From each patient, at the relevant time points indicated in the study calendar, blood will be withdrawn directly into two 10 mL lavender-topped (EDTA coated) tubes. Samples will be stored and assays run at the Human Immune Monitoring Core (Director: [name] laboratory at UC Davis).

Contact information listed below:

Human Immune Monitoring Core ([name] Laboratory)
UC Davis School of Medicine
[name]
[name]
LAB: [contact]

The HIMC laboratory (Director: [name]) is a research laboratory at UC Davis with both immunology expertise and the appropriate equipment to carry out the proposed studies. These studies will include: Luminex Cytokine Assays to determine changes

in cytokine profiles in response to treatment and Flow Cytometry to detect changes in immune cell subsets.

The tubes should be centrifuged as soon as possible at approximately 800 x g for 10 minutes. Plasma should be transferred to a 15 mL conical tube and centrifuged a second time at 1000 – 1500 x g for 10 minutes. After the second centrifugation, aliquot plasma in 500 ul aliquots into labeled cryovials. For peripheral blood mononuclear cell (PBMC) preparation, replace the plasma removed with an equal amount of PBS (Ca and Mg free) in the original lavender-top tubes, and then slowly layer it on top of the 15ml of Ficoll in a 50ml conical tube, followed by centrifugation at 800 x g for 20 minutes with the break off. The buffy coat, a whitish layer of cells between the PBS and Ficoll layers above the red blood cell layer, should be collected and transferred into a new 50ml tube, washed once with 50ml of PBS, re-suspended in an appropriate volume of freezing medium and then transferred into labeled cryovials (10⁷/ml/vial). All cryovials are then to be frozen as rapidly as possible, and stored in a -70 degree freezer until batch analysis is feasible by the HIMC.

Sites other than UC Davis may store per SOP until ready for shipment to UC Davis HIMC. Please contact [name] lab prior to shipment.

7.3 Withdrawal/Discontinuation

When a subject discontinues/withdraws prior to trial completion, all applicable activities scheduled for the final trial visit should be performed at the time of discontinuation. Any adverse events which are present at the time of discontinuation/withdrawal should be followed in accordance with the safety requirements outlined in Section 5.4 Attribution of adverse events and Section 7.5 - Assessing and Recording Adverse Events. Subjects who a) attain a CR or b) complete 24 months of treatment with MK-3475 may discontinue treatment. After discontinuing treatment following assessment of CR, these subjects should return to the site for a Safety Follow-up Visit and then proceed to the Follow-Up Period of the study.

7.4 Visit Requirements

Visit requirements are outlined in Section 6.0 - Trial Flow Chart. Specific procedure-related details are provided above in Section 7.1 - Trial Procedures.

7.4.1 Screening

Visit requirements are outlined in Section 6.0 - Trial Flow Chart. Specific procedure-related details are provided above in Section 7.1 - Trial Procedures.

Approximately 30 days prior to enrollment, potential subjects will be evaluated to determine that they fulfill the entry requirements as set forth in Section 5.1. Written consent must

be obtained prior to performing any protocol specific procedure. Results of a test performed prior to the subject signing consent as part of routine clinical management are acceptable in lieu of a screening test if performed within the specified time frame. Screening procedures are to be completed within 30 days prior to the first dose of trial treatment except for the following:

Laboratory tests are to be performed within 10 days prior to the first dose of trial treatment. For women of reproductive potential, a urine pregnancy test will be performed within 72 hours prior to first dose of trial treatment. If urine pregnancy results cannot be confirmed as negative, a serum pregnancy test, performed by the local study site laboratory, will be required.

Tumor imaging must be performed within 30 days prior to the first dose of trial treatment.

7.4.2 Treatment Period

Visit requirements are outlined in Section 6.0 - Trial Flow Chart. Specific procedure-related details are provided above in Section 7.1 - Trial Procedures.

7.4.3 Post-Treatment Visits

7.4.3.1 Safety Follow-Up Visit

The mandatory Safety Follow-Up Visit should be conducted approximately 30 days after the last dose of trial treatment or before the initiation of a new anti-cancer treatment, whichever comes first. All AEs that occur prior to the Safety Follow-Up Visit should be recorded. Subjects with an AE of Grade > 1 will be followed until the resolution of the AE to Grade 0-1 or until the beginning of a new anti-neoplastic therapy, return to baseline, or it is deemed that further recovery is unlikely, whichever occurs first. SAEs that occur within 30 days of the end of treatment or before initiation of a new anti-cancer treatment should also be followed and recorded.

7.4.3.2 Follow-up Visits

Every effort should be made to collect information regarding disease status until the start of new anti-neoplastic therapy, disease progression, death, end of the study. Information regarding post-study anti-neoplastic treatment will be collected if new treatment is initiated.

7.4.3.2.1 Survival Follow-up

Once a subject experiences confirmed disease progression or starts a new anti-cancer therapy, the subject moves into the survival follow-up phase and should be contacted by telephone every 12 weeks to assess for survival status until death, withdrawal of consent, or the end of the study, whichever occurs first.

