5.1.5.3 Dose Modification

Adverse events (both non-serious and serious) associated with pembrolizumab exposure may represent an immunologic etiology. These adverse events may occur shortly after the first dose or several months after the last dose of treatment. MK-3475 will be withheld for MK-3475-related toxicities and severe or life-threatening AEs as per Table 5. See Section 5.6.1 and Events of Clinical Interest Guidance Document for supportive care, including use of corticosteroids.

Table 5: Dose modification guidelines for MK-3475 related adverse events.

Toxicity	Hold Treatment For Grade	Timing for Restarting Treatment	Treatment Discontinuation
Diarrhea/Colitis	2-3	Toxicity resolves to Grade 0-1	Toxicity does not resolve within 12 weeks of last dose or inability to reduce corticosteroid to 10 mg or less of prednisone or equivalent per day within 12 weeks
	4	Permanently discontinue	Permanently discontinue
AST, ALT, or Increased Bilirubin	2	Toxicity resolves to Grade 0-1	Toxicity does not resolve within 12 weeks of last dose
	3-4	Permanently discontinue (see exception below) ^a	Permanently discontinue
Type 1 diabetes mellitus (if new onset) or Hyperglycemia	T1DM or 3-4	Hold pembrolizumab for new onset Type 1 diabetes mellitus or Grade 3-4 hyperglycemia associated with evidence of beta cell failure	Resume pembrolizumab when patients are clinically and metabolically stable
Hypophysitis	2-4	Toxicity resolves to Grade 0-1. Therapy with pembrolizumab can be continued while endocrine replacement therapy is instituted	Toxicity does not resolve within 12 weeks of last dose or inability to reduce corticosteroid to 10 mg or less of prednisone or equivalent per day within 12 weeks
Hyperthyroidism	3	Toxicity resolves to Grade 0-1	Toxicity does not resolve within 12 weeks of last dose or inability to reduce corticosteroid to 10 mg or less of prednisone or equivalent per day within 12 weeks
	4	Permanently discontinue	Permanently discontinue
Hypothyroidism		Therapy with pembrolizumab	Therapy with pembrolizumab can be continued

Toxicity	Hold Treatment For Grade	Timing for Restarting Treatment	Treatment Discontinuation
Infusion Reaction		can be continued while thyroid replacement therapy is instituted	while thyroid replacement therapy is instituted
	2 ^b	Toxicity resolves to Grade 0-1	Permanently discontinue if toxicity develops despite adequate premedication
	3-4	Permanently discontinue	Permanently discontinue

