7.5.3 Immediate Reporting of Adverse Events to Merck and BIPI

7.5.3.1 Serious Adverse Events

A serious adverse event is any adverse event occurring at any dose or during any use of Merck's product that:

- Results in death;
- Is life threatening;
- Results in persistent or significant disability/incapacity;
- Results in or prolongs an existing inpatient hospitalization;
- Is a congenital anomaly/birth defect;
- Is another important medical event

Note: In addition to the above criteria, adverse events meeting either of the below criteria, although not serious per ICH definition, are reportable to the Merck in the same timeframe as SAEs to meet certain local requirements. Therefore, these events are considered serious by Merck for collection purposes.

- Is a new cancer (that is not a condition of the study);
- Is associated with an overdose.

Refer to Table 12.7 for additional details regarding each of the above criteria.

For the time period beginning when the consent form is signed until treatment allocation, any serious adverse event, or follow up to a serious adverse event, including death due to any cause other than progression of the cancer under study (Section 7.2.3.3 for additional details) that occurs to any subject must be reported within 2 working days to Merck Global Safety if it causes the subject to be excluded from the trial, or is the result of a protocol-specified intervention, including but not limited to washout or discontinuation of usual therapy, diet, placebo treatment

or a procedure.

Progression of the cancer under study is not considered an adverse event unless it results in hospitalization or death.

For the time period beginning at treatment allocation, through 90 days following cessation of treatment, or 30 days following cessation of treatment if the subject initiates new anti-cancer therapy, whichever is earlier, any serious adverse event, or follow up to a serious adverse event, including death due to any cause other than progression of cancer under study (reference Section 7.5.4 for additional details), whether or not related to Merck product, must be reported within 2 working days to Merck Global Safety.

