Additionally, any serious adverse event, considered by an investigator who is a qualified physician to be related to Merck product that is brought to the attention of the investigator at any time following consent through the end of specified safety follow-up period specified in the paragraph above, or at any time outside of the time period specified in the previous paragraph also must be reported immediately to Merck Global Safety.

SAE reports and any other relevant safety information are to be forwarded to the Merck Global Safety [contact]

Assessment of safety laboratory parameters

A copy of all 15 Day Reports and Annual Progress Reports is submitted as required by FDA, European Union (EU), Pharmaceutical and Medical Devices agency (PMDA) or other local regulators. Investigators will cross reference this submission according to local regulations to the Merck Investigational Compound Number (IND, CSA, etc.) at the time of submission. Additionally investigators will submit a copy of these reports to Merck & Co., Inc. (Attn: Worldwide Product Safety; [contact]) at the time of submission to FDA.

All subjects with serious adverse events must be followed up for outcome.

The investigator shall report all SAEs and non serious AEs relevant to a reported SAE by fax from the time the informed consent is signed until the trial specified observational period (please specify) using BI IIS SAE form to BIPI Unique Entry Point in accordance with the following timelines:

- within five (5) calendar days upon receipt of initial and follow-up SAEs containing at least one fatal or immediately life-threatening event;
- within ten (10) calendar days upon receipt of any other initial and follow-up SAEs.

BI Unique Entry point:

Boehringer Ingelheim Pharmaceuticals, Inc
[name]
[name]

[contact]

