7.5.3.2 Events of Clinical Interest

Selected non-serious and serious adverse events are also known as Events of Clinical Interest (ECI) and must be reported within 2 working days to Merck Global Safety. (Attn: Worldwide Product Safety; [contact])

For the time period beginning when the consent form is signed until treatment allocation, any ECI, or follow up to an ECI, that occurs to any subject must be reported within 2 working days to Merck Global Safety if it causes the subject to be excluded from the trial, or is the result of a protocol-specified intervention including but not limited to washout or discontinuation of usual therapy, diet, placebo treatment or a procedure.

For the time period beginning at treatment allocation through 90 days following cessation of treatment, or 30 days following cessation of treatment if the subject initiates new anticancer therapy, whichever is earlier, any ECI, or follow up to an ECI, whether or not related to Merck product, must be reported within 24 hours to Merck Global Safety.

Events of clinical interest for this trial include:

1. an overdose of Merck product, as defined in Section 7.2.1 - Definition of an Overdose for This Protocol and Reporting of Overdose to Merck, that is not associated with clinical symptoms or abnormal laboratory results.
2. an elevated AST or ALT lab value that is greater than or equal to 3X the upper limit of normal and an elevated total bilirubin lab value that is greater than or equal to 2X the upper limit of normal and, at the same time, an alkaline phosphatase lab value that is less than 2X the upper limit of normal, as determined by way of protocol-specified laboratory testing or unscheduled laboratory testing.*

***Note:** These criteria are based upon available regulatory guidance documents. The purpose of the criteria is to specify a threshold of abnormal hepatic tests that may require an additional evaluation for an underlying etiology.

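### Patients who stop for progression and start no new therapy have no scheduled adverse-event question after Day 30, though SAEs and ECIs are reportable to Day 90, so late immune events may be under-counted

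*Combined protocol and SAP*

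**What the plan says.** **Reporting duty.** Section 7.5.3.1 requires SAEs, related or not, to be reported "through 90 days following cessation of treatment, or 30 days following cessation of treatment if the subject initiates new anti-cancer therapy, whichever is earlier". Section 7.5.3.2 sets the same 90/30-day rule for ECIs, and the guidance document in Section 12.9 names immune-related events as the main kind of ECI. Beyond that period, an SAE judged related to the Merck product and noticed "at any time outside of the time period specified in the previous paragraph also must be reported immediately to Merck Global Safety".

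**Expected timing.** Section 5.1.5.3 warns that immune-type events can appear "several months after the last dose of treatment".

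**Scheduled contact.** The Safety Follow-Up Visit (7.4.3.1) is "conducted approximately 30 days after the last dose of trial treatment", or earlier if new therapy begins. Section 5.8 gives 30 days of adverse-event monitoring after treatment, and reserves disease-status follow-up for patients who stop for a reason other than progression. In the flow chart (6.1), the last adverse-event review mark is in the column that combines the discontinuation visit, the safety visit and PFS follow-up. There is no survival follow-up column. Once progression is confirmed, Section 7.4.3.2.1 says the patient "should be contacted by telephone every 12 weeks to assess for survival status until death, withdrawal of consent, or the end of the study". It does not say from which date the 12 weeks are counted.

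**The concern.** The plan asks sites to report serious and immune events over a period in which, for one group of patients, nobody is scheduled to ask about them. That group is patients who came off treatment for progression and have not yet started another therapy. Their reportable window runs to Day 90, but the only later contact is a call about whether they are alive.

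Safety and tolerability of the combination is the primary objective (3.1). The RP2D rests on toxicity seen in both the de-escalation and expansion parts (5.1.5.2, 8.1), and toxicity is one criterion for choosing between Cohorts A and B (8.1). With at most 38 patients, one event is 1/38 = 2.6% of the total. In a cohort of 10 it is 10 percentage points. A small number of late events that go unrecorded could therefore change the toxicity summary.

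**Working it through.** The plan states no rate or count of late events, so there is no figure to reproduce. The check compares the reporting windows with the contact schedule and does the day arithmetic.

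**Step 1: the part of the window with no scheduled question.** Inputs are the 90-day window (7.5.3.1, 7.5.3.2) and the visit at about Day 30 (7.4.3.1).
- 90 − 30 = 60 days (Days 31 to 90), which is two thirds of the window, for a progressor without new therapy.
- For a progressor who starts new therapy, the window closes at Day 30 and this mismatch does not arise. Only the open-ended duty to report related SAEs remains, also without a scheduled question.
- A patient who stops for another reason keeps disease-status follow-up, which shares the flow-chart column carrying the adverse-event review.

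**Step 2: where the first survival call falls.** 12 weeks × 7 = 84 days.
- Counted from the last dose: Day 84, inside the window by 6 days.
- Counted from the Day 30 visit: 30 + 84 = Day 114, which is 24 days after the window has closed.

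Either reading fits the text, and in both the stated purpose of the call is survival status alone.

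**Step 3: the windows side by side.**

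| Place | What is reported after treatment | Limit |
|---|---|---|
| 1.0, Duration of Participation | new drug-related events | 30 days |
| 7.4.3.1 | SAEs | 30 days, or start of new therapy |
| 7.5 | all adverse events | 30 days |
| 7.5, on-treatment definition | later events only if related to drug or trial procedure | after Day 28 |
| 7.5.3.1 | SAEs regardless of relationship | 90 days (30 if new therapy) |
| 7.5.3.2 | ECIs regardless of relationship | 90 days (30 if new therapy) |

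An unrelated SAE on Day 60 in a patient without new therapy is reportable under 7.5.3.1 but not under the Day 28 sentence in 7.5. A question added to the call would not settle what the site should do with the answer.

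**Step 4: illustration of size, on assumed values only.** Let N be the patients exposed to the gap, p the chance of a new SAE in Days 31 to 90, and c the share that reaches the site unprompted. Expected missed events are N·p·(1 − c), and the chance of missing at least one is 1 − [1 − p(1 − c)]^N. None of p, c or N is in the documents. N = 38 is the maximum enrolment and so an upper bound. Take c = 0.5.
- N = 38, p = 0.03: 38 × 0.03 × 0.5 = 0.57 missed; 1 − 0.985^38 = 44%.
- N = 38, p = 0.10: 38 × 0.10 × 0.5 = 1.9 missed; 1 − 0.95^38 = 86%.
- N = 20, p = 0.03: 20 × 0.03 × 0.5 = 0.3 missed; 1 − 0.985^20 = 26%.
- N = 20, p = 0.10: 20 × 0.10 × 0.5 = 1.0 missed; 1 − 0.95^20 = 64%.

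A spread of 0.3 to 1.9 events from plausible-looking inputs shows that the under-count cannot be sized from this plan.

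**The case against.** The plan does provide for late events.
- Section 7.1.2.1 has adverse events graded and recorded through the follow-up period.
- Section 5.5.1 asks for concomitant medication beyond 30 days to be recorded for SAEs and ECIs.
- Section 7.5 keeps drug-related events reportable after Day 28, and 7.5.3.1 does so for related SAEs without a time limit. Late immune toxicities are likely to be among the related ones.
- Adverse events already open are followed toward resolution (1.0, 7.4.3.1, 7.5).
- Section 10.9 requires a Follow-Up Form (IH-302) after each required follow-up encounter. Its contents are not in the documents, so it may already prompt for such events.
- The 90-day rule is a duty to report to the drug supplier, and Section 8 does not tie the toxicity summary to Day 90.

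All of this stands, and it limits the conclusion. None of it schedules an enquiry for new events after Day 30 in the affected patients. Each provision says what to do with an event once the site knows of it.

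A reader might infer that late immune events *will* be under-counted, or that every patient who progresses has a 90-day window with nobody asking. The documents support neither. Unprompted reports still count, no late-event rate is given, and the window ends at Day 30 for anyone who starts new therapy, which is a likely course after progression. A reader might also infer that the MTD is at risk. It is not, because DLTs are counted in Cycle 1 (5.3).

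**Conclusion.** The point holds for patients who stop for progression and have not started new anti-cancer therapy. For them, Days 31 to 90 of the SAE and ECI window depend on passive capture, and late immune events may be under-counted. This follows from the text and needs no assumed rate. The number of patients affected and of events missed cannot be derived from the documents, and the figures in the illustration carry no weight beyond showing that. DLT counts, the MTD, sample size and the response rule are untouched. What could be affected is the overall toxicity description, and through it the judgement on RP2D and the comparison of the two cohorts. The conflict among the 28-, 30- and 90-day windows is a separate, certain defect, and it has to be resolved for any added question to be useful. This is an inexpensive improvement, not a flaw that undermines the trial.

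**What to change.** 1. Reconcile the post-treatment reporting periods in Section 1.0 (Duration of Participation), 7.4.3.1, 7.5, 7.5.3.1 and 7.5.3.2. State one window, whether it covers unrelated events, and how the new-therapy cut-off works when that therapy starts between Day 31 and Day 90.
2. In 7.4.3.2.1, count the first survival call from the last dose and place it at the end of the chosen window (about Day 90 if the 90-day rule is kept). Add a short scripted question covering hospitalization, new systemic steroid use, and new serious or suspected immune events since the Day 30 visit. Record the answers on the existing Follow-Up Form (IH-302), and add the contact to the flow chart in 6.1.

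The cost is a few minutes on one telephone call. Depending on how sites now count the 12 weeks, it may be a re-timed or an additional call. No clinic visit or procedure is added, and no change to sample size or analysis is needed.
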